8.4 Follow-up of Adverse Events

Serious Adverse Events will be followed up by the site paediatrician co-investigator until their resolution or stabilisation or until causality is determined to be unrelated to trial interventions. The outcome will be assessed as:

- Recovered/resolved
- Not recovered/not resolved
- Recovering/resolving
- Recovered with sequelae/resolved with sequelae
- Fatal

8.5 Assessment of Causes of Death

An endpoint review committee, comprising two individuals experienced in paediatric care in sub-Saharan Africa, will review all clinical, laboratory and radiological information for neonates who die during the trial to determine the causes of death that will be used in the final analysis. The endpoint review committee will remain blinded to the randomised allocations.

8.6 Reporting of SAEs & SUSARS

Information for the SAE forms will be collected as part of routine outcome data collection by the research team. The Data and Safety Monitoring Board (DSMB) will receive a summary of SAEs after 1 month of recruitment, then move to three- or six-monthly; the DSMB will decide the frequency following the first report. The DSMB will note these and, unless there is a special cause of concern, will consider them as part of the planned DSMB meetings which will discuss interim analyses. All SAEs will also be reported to the Sponsor and ethical review committees (MRC/UVRI and LSHTM) as part of their respective annual progress and safety report.

In addition, if any other serious *but unexpected* adverse event occurs, which might be related to a trial intervention, a written SAE report should be submitted to the ethical review committees (MRC/UVRI and LSHTM) within 48 hours of the investigators becoming aware of the event with a follow-up report provided within a further five working days. This expedited reporting will be limited to those outcomes not already listed as primary or secondary outcomes, yet which might reasonably occur as a consequence of the trial intervention.

It may be necessary to take appropriate urgent safety measures to protect participants from any immediate hazard to their health and safety. These measures will be taken immediately. It is not necessary to wait for ethical approval before implementing the safety measure; however, both ethical review committees and the Sponsor will be informed in writing within three working days by submitting a substantial amendment.

8.7 Data and Safety Monitoring Board

A Data Safety and Monitoring Board (DSMB) will oversee the overall integrity of the study, its safety and its continued relevance and ability to answer the primary objective.

The DSMB will meet approximately yearly during the study.

Chair: [name], Professor of Statistical Epidemiology, National Perinatal Epidemiology Unit, University of Oxford, Oxford, UK

Members:

- [name], Consultant Neonatologist, Department of Paediatrics and Child Health, University of Cape Town, Cape Town, South Africa
- [name], Professor of Bioethics, Nuffield Department of Population Health, University of Oxford, Oxford, UK

8.8 Stopping Criteria

The DSMB will regularly monitor all data to consider any potential harm to participants. Formal rules for stopping due to harm will be discussed with the DSMB at their first meeting.

8.9 Interim Analyses

An interim analysis will be performed on the primary outcome when approximately half of neonates have been randomised (around 1 year into the trial). An earlier interim analysis may be carried out if requested by the DSMB. The DSMB will have access to all data. An independent statistician will perform the interim analysis, blinded to treatment allocation, and report to the DSMB. The Chair of the DSMB may request additional meetings/analyses, as he or she feels necessary. In the light of these data and other evidence from relevant studies, the DSMB will inform the TSC if in their view:

- i. It is evident that no clear outcome will be obtained with the current trial design.
- ii. They have a major ethical or safety concern.
- iii. It is evident that the intervention is clearly superior and continuing the trial would be unethical to those in the control arm.

9. Discontinuation Criteria

9.1 Criteria for stopping the intervention

Those neonates under close monitoring who meet any of the following criteria at any point during enrolment will be temporarily withdrawn from the intervention and kept in an open warmer or an incubator based on the discretion of the on-duty study paediatrician:

Stopping criteria:

Severely unstable for >10 minutes if:

- $\text{SpO}_2 < 88\%$ in oxygen

AND ≥ 1 of:

- Respiratory rate <20 or > 100 breaths/min
- Apnoea requiring bag-mask ventilation
- HR <100 or >200 bpm

Any other condition which precludes continuous skin-to-skin contact:

- Severe jaundice requiring immediate management
- Severe anaemia requiring blood transfusion
- Active seizures
- Severe abdominal distension
- Omphalitis or infection of the umbilical cord
- Apnoea requiring bag-valve-mask ventilation
- Widespread skin infection of baby or caregiver providing skin-to-skin contact
- Mother or caregiver not available or willing to do continuous skin-to-skin contact

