3.2.6 Concomitant Therapies and Medications

All enrolled neonates will receive clinically indicated treatments, including but not limited to oxygen, IV fluids, antibiotics, aminophylline, anticonvulsant medicines, and phototherapy. Standardised clinical guidelines will be followed for common neonatal conditions, including preterm fluids/feeding (including breastfeeding), presumed and proven sepsis, respiratory distress, jaundice, and seizures. Bubble CPAP will be provided at the discretion of the on-duty paediatrician, if this is local standard of care. Jaundice will be treated with phototherapy for neonates in both arms. All caregivers will be trained in KMC regardless of study arm.

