4.2.2 Exclusion criteria

- Result of multifetal pregnancy (triplets and above, unless triplet pregnancy resulted in demise/stillbirth of one or more fetuses)
- Indication for KMC “certain” according to WHO guidelines: pragmatically defined as clinically well neonates receiving none of the above therapy-based criteria
- Severely life-threatening instability defined as $\text{SpO}_2 < 88\%$ in oxygen AND ≥ 1 of:
 - Respiratory rate < 20 or > 100 breaths/min
 - Apnoea requiring bag-mask ventilation
 - HR < 100 or > 200 bpm
- Severe jaundice requiring immediate management
- Active neonatal seizures
- Major congenital malformation
- Parent does not provide written informed consent to participate in trial (Appendix A)

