5.7.1 Delivering the intervention arm

KMC will be initiated as soon as possible following randomisation. Neonates allocated to the intervention arm will be naked except for hat and diaper. They will be secured to the exposed chest of the mother/caregiver using a KMC wrap. Prior to placing the neonate in the skin-to-skin position, a study nurse or medical officer will attach a pulse oximetry probe to the hand and a temperature probe to the torso. These procedures will take place in the admission area, prior to moving the baby to the study area. On arrival at the study area, the mother/caregiver will be seated on an adjustable bed. If required, oxygen will be provided from a cylinder or concentrator (depending on available resources at each site). Oxygen will be delivered to the neonate via nasal cannula or mask (if CPAP is required). If IV fluids are required, a bag of IV fluids will be hung and an IV cannula will be placed by a study nurse or medical officer. The study nurse or medical officer will then initiate IV fluids, with drip rate calculated according to standardised guidelines. If the mother/caregiver needs to take a short break (e.g., to shower or use the restroom), the neonate will be placed in an incubator or under a radiant heater. Every effort will be made to encourage skin-to-skin contact for 18h/day, unless otherwise clinically indicated. While we anticipate the mother will be the primary KMC provider, a family member or close friend (helper) may also provide skin-to-skin care in order to avoid disruptions. Clinical study staff at each site will counsel mothers/caregivers about KMC throughout the hospital stay, including the time of discharge. In addition, mothers who practised KMC as participants may be engaged as peer-counsellors when they return for follow-up. For each episode of skin-to-skin contact, the caregiver providing KMC (e.g., mother, father, helper) and the time of initiation and duration will be monitored and recorded in the electronic CRF (using bedside tablets).

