9.2 Criteria for restarting intervention

If a neonate is temporarily withdrawn for any of the above reasons, the intervention can be restarted once all the following criteria are met:

- No longer fill the stopping criteria
- No apnoea requiring bag-mask ventilation for 24h
- Not on phototherapy
- No seizures for 24 hours
- No abdominal distension
- Mother or caregiver available and willing to do skin-to-skin contact
- No healthcare worker concerns about clinical condition

10. Sample Size and Analysis Plan

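### The KMC entry, stopping and restart rules do not agree: one apnoea has two stopping thresholds, four stopping conditions are not exclusions, and restart is blocked by states that do not stop KMC

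*Protocol*

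**What the plan says.** **Entry (4.2.2).** The exclusion that begins "Severely life-threatening instability defined as" needs SpO2 below 88% in oxygen together with at least one further sign. One of those signs is "Apnoea requiring bag-mask ventilation". Separate exclusions cover "Severe jaundice requiring immediate management", active seizures and major malformation.

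**Start (5.7.1).** "KMC will be initiated as soon as possible following randomisation".

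**Stopping (9.1).** A baby who meets any listed criterion, at any point during enrolment, is temporarily withdrawn from KMC. The list repeats the entry composite with a duration of more than 10 minutes. It then gives standalone items, among them "Apnoea requiring bag-valve-mask ventilation", severe anaemia needing transfusion, severe abdominal distension, omphalitis, widespread skin infection, and a caregiver who is unavailable or unwilling.

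**Restart (9.2).** After a withdrawal for any of those reasons, every restart item must be met. They include "No apnoea requiring bag-mask ventilation for 24h", "Not on phototherapy", 24 hours without seizures and no abdominal distension.

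**Related text.** Section 3.2.6 says "Jaundice will be treated with phototherapy for neonates in both arms". Section 3.2.3 covers a mother's absence with no substitute: the baby goes to an incubator or heater until she or another family member comes back.

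**The concern.** These rules decide who receives the allocated care, and they act only on the KMC arm. Where two sections give different answers for the same baby, staff have to choose one, and the protocol gives no basis for the choice.

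The babies concerned are the sicker ones, and the primary outcome is death within 7 days. Time held off KMC weakens the contrast under intention to treat. It also feeds into the per-protocol and complier analyses of section 10.2.4 and the exploratory analyses of mortality by time of initiation and continuity of KMC in section 10.2.3. In those analyses, a hold caused by an ambiguous rule would be mixed with a hold caused by the baby's condition or the caregiver's choice.

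**Working it through.** The point is textual, so the first check sets the lists side by side.

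| Condition | Entry (4.2.1, 4.2.2) | Stopping (9.1) | Restart (9.2) |
|---|---|---|---|
| Apnoea needing bag-mask ventilation | Only with SpO2 <88% in oxygen | (a) With SpO2 <88% in oxygen, >10 min; (b) on its own | None for 24 h |
| Severe anaemia needing transfusion | Not listed | Stops | General item only |
| Abdominal distension | Not listed | Severe only | Any degree blocks |
| Omphalitis or cord infection | Not listed | Stops | General item only |
| Widespread skin infection | Not listed | Stops | General item only |
| Seizures | Active | Active | None for 24 h |
| Severe jaundice needing immediate management | Excluded | Stops | General item only |
| Phototherapy | Not listed | Not listed | Blocks |
| Caregiver | Able and willing | Stops if unavailable or unwilling | Available and willing |

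The general item is that the baby no longer meets the stopping criteria. All restart items apply together.

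1. **Within 9.1.** Any baby who meets the apnoea limb of composite (a) already meets (b), so that limb never decides anything. The SpO2 and duration conditions in (a) have no effect for apnoea if (b) stands. If (a) was meant to govern, (b) contradicts it.

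2. **Entry against stopping.** Five standalone stopping items have no matching exclusion: apnoea alone and the four conditions named above. For those four, a baby with the condition present at allocation satisfies 4.2.2, is to start under 5.7.1, and is to be withdrawn under 9.1 at the same moment. For apnoea alone the overlap is narrow: ventilation would have to be needed at allocation with SpO2 of 88% or more in oxygen.

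3. **Stopping against restart.** Phototherapy and non-severe distension are compatible with continuing KMC but not with resuming it. Consider a baby on phototherapy for non-severe jaundice. KMC may start and continue. If the caregiver becomes unavailable, 9.1 counts this as a withdrawal, and 9.2 read literally keeps the baby off KMC until phototherapy ends. Section 3.2.3 returns the same baby to KMC when the caregiver returns.

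**Size, as illustration only.** The protocol's base case is 25% against 19.4% mortality (5.6 points), 80% power and 5% significance, taken as two-sided because the text does not say. With p̄ = 0.222,

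n = [1.96√(2p̄(1−p̄)) + 0.842√(p₁(1−p₁) + p₂(1−p₂))]² / 0.056² = 864 per arm,

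which reproduces the stated 875 to within 3%. Inflation also reproduces: 875/0.80 = 1093.75, stated as 1094.

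Assume a share f of the KMC arm gains nothing and carries average risk. The difference becomes 5.6(1−f) points:

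| Assumed f | Difference (points) | Power, 875 per arm | Power, 1094 per arm |
|---|---|---|---|
| 0% | 5.60 | 80.5% | 88.4% |
| 5% | 5.32 | 76.2% | 84.8% |
| 10% | 5.04 | 71.4% | 80.7% |

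No value of f comes from the protocol.

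**The case against.** The strongest reply is that exclusion, stopping and restart rules serve different purposes. A stricter rule for resuming after a deterioration than for first entry can be a deliberate safety margin. That stands for the 24-hour seizure and apnoea items, and perhaps for severe distension to stop and none to resume. It does not explain the double apnoea entry in 9.1, or why a caregiver's absence should trigger clinical restart conditions.

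A reader might infer that a baby who fails a restart item at screening is barred from KMC altogether. The text does not support this: 9.2 applies only after a withdrawal, so phototherapy or a recent seizure at screening does not prevent a first session. Nor is there a conflict for a baby ventilated for apnoea before screening whose condition has recovered. That baby meets no stopping criterion at allocation, and the same event afterwards is an on-treatment event.

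Part of the phototherapy gap is already covered. The Definitions describe severe jaundice broadly, and severe jaundice needing immediate management both excludes and stops. What remains is phototherapy for less severe jaundice.

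There is also some flexibility. Section 5.7.1 qualifies the skin-to-skin target by clinical indication, and 9.1 mentions the paediatrician's discretion. It is unclear whether that discretion covers the withdrawal itself or only the choice between warmer and incubator.

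Finally, section 10.1 already allows 10% for withdrawal due to deterioration or withdrawn consent, and 10% for dilution from noncompliance and loss to follow-up. Some of the holds described here may fall within those allowances.

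**Conclusion.** The point holds as an inconsistency in the rules for delivering the allocated care. Section 9.1 gives one event two incompatible thresholds. Four stopping conditions can be present in an eligible baby who is told to start KMC. After any withdrawal, including one for caregiver absence, restart is blocked by states that do not themselves stop KMC, against section 3.2.3.

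The number of babies affected is unknown, and the power figures above rest on assumed shares and average risk. It would be tempting to conclude that the trial is underpowered. The protocol does not show that: the allowances in section 10.1 may absorb part of the loss, and under intention to treat the effect is dilution towards no difference.

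It would also be wrong to set the 24-hour apnoea hold against the 12 hours in which section 18 says 66% of deaths fell in the earlier Ethiopian trial. Those hours run from birth, whereas this hold runs from the last event in babies screened at up to 48 hours of age.

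The change is worth making because it is cheap and the rules bear on safety in one arm only.

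**What to change.** The sponsor's clinical team should reconcile sections 3.2.3, 3.2.6, 4.2.2, 5.7.1, 9.1 and 9.2, preferably in one table. Each condition should have a single definition and a stated status at four points: entry, first initiation of KMC, stopping and restart. The table should settle:

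- which of the two apnoea entries in 9.1 applies, and how it relates to the entry composite;
- what happens when a standalone stopping condition is present at allocation;
- how phototherapy and the degree of abdominal distension are treated at each point;
- whether the restart list applies after a caregiver's absence;
- what the paediatrician's discretion in 9.1 covers.

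Which rule to adopt is for the clinical team, and none is proposed here. Where an asymmetry is intended, one sentence saying so is enough. The conditions should also be recorded at screening in both arms, so that the share affected can be reported and compared on an equal footing.

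The cost is a protocol amendment and a short site checklist. Depending on what is decided, a few babies may become ineligible or start later.

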9.2 Criteria for restarting intervention

If a neonate is temporarily withdrawn for any of the above reasons, the intervention can be restarted once all the following criteria are met:

- No longer fill the stopping criteria
- No apnoea requiring bag-mask ventilation for 24h
- Not on phototherapy
- No seizures for 24 hours
- No abdominal distension
- Mother or caregiver available and willing to do skin-to-skin contact
- No healthcare worker concerns about clinical condition

10. Sample Size and Analysis Plan

10.1 Sample Size

Surveillance data collected on admissions to the JH neonatal unit between January and December 2016 (Perinatal Audit Data from Uganda Paediatric Association) suggest that the mortality rate in the control arm will be at least 25% across the four sites. The most recent Cochrane review and a metaanalysis demonstrated large mortality reductions among stable neonates (RR 0.60 and 0.64 respectively) (2,3), and the RCT in Ethiopia published a RR for mortality amongst neonates before stabilisation of 0.57 (4). Assuming a conservative control mortality rate of 25% across the 4 hospitals in our study, 1750 neonates (875 per arm) would enable us to detect a relative difference between arms of 22.4% (5.6% absolute difference) with 80% power and a significance level of 5%. If the control mortality rate were in fact as low as 18%, we would still be able to detect a relative difference of 27% (absolute difference of 4.8%). We plan to recruit 2188 neonates (1094 per arm) in order to allow for 10% withdrawal due to clinical deteriorations and consent withdrawal, and 10% dilution due to

noncompliance and loss to follow-up. This sample size would enable us to detect absolute reductions of 6.3% and 5.4% from control rates of 25% and 18%, respectively, with 90% power. Results from the feasibility study suggest that ≥ 400 eligible neonates are admitted to JH per year. Preliminary data suggest ~ 500 eligible neonates each are admitted to IH and EH per year and ~ 800 eligible neonates are admitted to MH per year. Recruitment will take place over 24 months, leading to an eligible population of ~ 4400 neonates. Thus, we have applied a conservative recruitment rate of $\sim 50\%$ to achieve the target sample of 2188. The admissions audit data from our feasibility study suggest that a higher recruitment rate should be achievable. Recruitment will continue until the target sample is reached, up to a maximum of 27 months, which includes a 3-month buffer period in case recruitment is delayed or slower than expected.

10.2 Analysis Plan for the Trial

10.2.1 Summary of baseline data and flow of patients

Baseline characteristics of enrolled neonates will be summarized by treatment arm. Descriptive statistics for continuous variables will include mean, SD, median, range, and number of observations. Categorical variables will be summarized as counts and proportions. Screening, enrolment, reasons for non-enrolment, randomisation, and loss to follow up will be detailed in a CONSORT diagram (68).

10.2.2 Primary and secondary outcome analyses

The primary and secondary outcome analyses will be carried out on all neonates as randomised ('intention to treat'). Analysis will follow a pre-specified analysis plan approved by the TSC and DSMB prior to unblinding the study database. The criterion for statistical significance at the final analysis will be $P < 0.05$. The rate of loss to follow up will be reported. We will report risk ratios for mortality seven days after enrolment (primary outcome) and 28 days after enrolment (secondary outcome) for intervention versus control with associated 95% confidence intervals. Secondary outcomes: time from intervention/control procedures starting to death and length of hospital stay, will be analysed using Kaplan-Meier plots and the hazard ratios with accompanying 95% CI calculated using Cox proportional hazards regression. All other secondary outcomes will be analysed using appropriate regression models accounting for the nature of the distribution of the outcome and results will be presented as appropriate effect sizes with a measure of precision (95% confidence intervals). Both unadjusted analyses and analyses adjusted for stratification factors will be carried out. Additional exploratory analyses will control for any baseline measures that appear to be imbalanced between arms.

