4.2 Eligibility Criteria for the Trial

Participants must meet the following inclusion criteria and not have any of the exclusion critieria to be able to participate in the trial.

4.2.1 *Inclusion criteria*

- Neonate admitted to JH, MH, EH, IH, or KNRH (inborn or outborn)
- Singleton, twin, or triplet (if triplet pregnancy resulted in demise/stillbirth of one or more fetuses)
- Birthweight $\geq 700\text{g}$ and $\leq 2000\text{g}$
- Chronological age 1-48 hours at time of screening
- Alive at time of recruitment
- Parent/caregiver able and willing to provide KMC
- Parent/caregiver willing to attend follow-up visit
- Indication for KMC “uncertain” according to WHO guideline concerning clinical stability: pragmatically defined as receiving ≥ 1 therapy: oxygen, CPAP, IV fluids, therapeutic antibiotics, phenobarbital

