5.6 Randomisation

Randomisation will take place following collection of necessary baseline data and before the intervention or control procedures start. The details of the randomisation method are outlined in section 3.2.1. In situations where both twins are eligible for enrollment, they will be allocated to the same arm.

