5.8 Follow-up

Participants will be followed daily while admitted to the hospital (see section 6.1.2 for additional details).

At the time of discharge, all parents/caregivers will be provided with an illustrated handout on neonatal danger signs and instructed to contact the site study team or seek medical help if their baby becomes unwell. All families will be provided with phone numbers to contact the study team and a study participant ID card. Parents/caregivers will receive UgSh 20,000 (per enrolled neonate) to cover the costs of transport home and they will be able to keep the KMC wrap, so they can continue KMC at home (parents/caregivers of babies in both arms will be encouraged to continue KMC at home).

All participants will be given an appointment to attend the neonatal follow-up clinic at the respective study site on day 28-30. Transport costs (UgSh 20,000 per enrolled neonate) will also be provided to cover the costs of return transport to the study site for the follow-up visit. At this visit, repeat cUS (KNRH and JH only) and anthropometry will be performed; feeding practices and outcomes (alive, dead, readmitted) will be documented; and the WCI and Maternal Infant Responsiveness Instrument (MIRI) questionnaires will be administered to mothers.

If participants are discharged prior to day 7, additional follow-up will be arranged according to study site:

- At KNRH and JH, participants will be given an additional appointment to attend the neonatal follow-up clinic on day 7, where repeat cUS will be performed and outcomes (vital status, readmitted) will be recorded. If day 7 falls on a weekend, participants will be phoned on day 7 to ascertain outcome and the appointment will be made for the closest working day (e.g., if day 7 is Saturday, appointment on Friday; if day 7 is Sunday, appointment on Monday).
- At IH and MH, participants will be phoned on day 7 to ascertain outcome (alive, dead, readmitted) and reminded to attend the neonatal follow-up clinic appointment on day 28-30.

If participants do not attend follow-up clinic, a telephone call will be made the same day to ascertain outcome and feeding practices and to arrange follow-up, either in the clinic or at the families' home, as soon as possible. Routine follow-up beyond the planned study follow-ups will be provided by the study site staff according to standard practice and clinical need of the baby.

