6.1.5 Procedures at follow-up

At the 28-30-day follow-up visit, we will record:

- Breastfeeding status
- Anthropometric measures (weight, OFC, length)

- SARS-CoV-2 signs/symptoms and testing status/results for mothers and babies recruited after 25 March 2020

For participants at KNRH EH and JH, repeat cUS will be performed at the 28-30-day visit (see Section 6.1.6 for additional details). For the MIRI, trained study staff will administer a brief, validated set of questions to all mothers at the 28-30-day visit.

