6.2.3 Evaluations at follow-up

At the 28-30 day follow-up appointment, trained study staff will readminister the WCI questionnaire to all mothers. In addition, they will ask questions to ensure that costs are captured for the entire neonatal period and to inquire about families' plans going forward.

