10.2.4 Definition of analysis population related to protocol non-adherence

As described above, intention to treat analyses will be conducted on the primary and secondary outcomes. All neonates will be included, regardless of protocol adherence, to prevent the effects of attrition bias.

We will also report results of per protocol analyses and complier average causal effects to account for children for whom major protocol violations were recorded such as those relating to non-compliance with the study treatments.

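### If section 10.2.2 is followed as written with no allowance for dependence, a mother of two enrolled twins supplies two identical well-being records and that outcome's interval is too narrow

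*Protocol*

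**What the plan says.** Protocol section 1.4.2 lists infant-caregiver attachment and women's well-being, both at 28 days, among the secondary outcomes.

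- **Analysis set.** Section 10.2.2: "The primary and secondary outcome analyses will be carried out on all neonates as randomised", labelled intention to treat. Section 10.2.4 repeats this for primary and secondary outcomes: "All neonates will be included, regardless of protocol adherence, to prevent the effects of attrition bias". Neither section excepts an outcome measured on the mother.
- **Respondent.** Section 5.8, on the day 28-30 visit: "the WCI and Maternal Infant Responsiveness Instrument (MIRI) questionnaires will be administered to mothers". Section 6.2.3 has staff "readminister the WCI questionnaire to all mothers", and section 6.1.5 describes the MIRI as "a brief, validated set of questions to all mothers at the 28-30-day visit".
- **Multiples.** Section 4.2.1 admits "Singleton, twin, or triplet (if triplet pregnancy resulted in demise/stillbirth of one or more fetuses"). Section 5.6: "In situations where both twins are eligible for enrollment, they will be allocated to the same arm".
- **Model.** For these two outcomes, section 10.2.2 asks for regression suited to the outcome's distribution, unadjusted and adjusted for the stratification factors. It refers to a separate analysis plan, which is not at hand. The protocol nowhere mentions clustering, robust variance or a mother-level analysis set.
- **Linkage.** Section 5.4.3 gives each mother or caregiver an enrolment number linked to the neonate's.

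**The concern.** The WCI describes the woman, not the baby. If the analysis file has one row per neonate, a mother with two enrolled twins supplies the same WCI score on two rows. The second row carries no new information, but an ordinary regression counts it as an independent observation. Because twins share an arm, the repetition does not cancel in the comparison between arms; it adds to the true variance of the difference.

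Two things would follow. The standard error would be understated, so the criterion of P<0.05 in section 10.2.2 would be easier to meet than it claims. Mothers of twins would also carry double weight in the arm means. The same applies to the MIRI if it is scored once per mother. If it is answered separately for each infant, the two scores are correlated rather than copied and the effect is smaller.

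**Working it through.** **The plan's own figure.** There is none to reproduce: the protocol gives no number for the WCI, the MIRI, the twin share or a within-pair correlation. From section 10.1 only the recruitment target of 2188 (1094 per arm) is used.

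**Inputs**
- t, the share of analysed neonates who belong to a co-enrolled pair: not in the protocol; assumed 10%, 20% or 30%.
- rho, the within-pair correlation of the analysed score: 1 for the WCI, because the value is the same; 0.5 assumed as an illustration for a MIRI scored per infant.
- Both twins in the same arm (section 5.6).
- Significance level 5% (section 10.2.2), taken as two-sided.

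**Variance.** An arm with n neonates has n(1−t) singles and nt/2 pairs. With outcome variance s², each pair's total has variance 2s²(1+rho). The arm mean then has variance

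s²[n(1−t) + (nt/2)·2(1+rho)]/n² = (s²/n)(1 + t·rho).

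The naive analysis uses s²/n. Therefore:

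- true SE / naive SE = √(1 + t·rho)
- naive interval width as a share of the correct width = 1/√(1 + t·rho)
- real two-sided error = 2[1 − Φ(1.96/√(1 + t·rho))]

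Example for the WCI at t = 20%: √1.2 = 1.095; 1/1.095 = 0.913; 1.96/1.095 = 1.79; error 7.4%.

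| t | WCI (rho = 1): SE ratio | Naive width / correct | Real error | MIRI per infant (rho = 0.5): real error |
|---|---|---|---|---|
| 10% | 1.049 | 0.953 | 6.2% | 5.6% |
| 20% | 1.095 | 0.913 | 7.4% | 6.2% |
| 30% | 1.140 | 0.877 | 8.6% | 6.8% |

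The naive WCI standard error is thus 4.7%, 8.7% and 12.3% too small.

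**Simulation check.** With 4000 runs, 1094 per arm and no true difference, duplicated records rejected in 6.6%, 7.2% and 8.7% of runs at t = 10%, 20% and 30%. One record per mother rejected in 5.9%, 4.5% and 5.1%. The simulation standard error near 5% is √(0.05·0.95/4000), about 0.3 percentage points. The 5.9% is somewhat high for that noise, so the conclusion rests on the formula, which the duplicated-record results follow.

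**The case against.** The strongest reply is that the quoted sentence is an intention-to-treat statement. It says who is included and by which allocation, not how a maternal questionnaire is laid out in the data. No passage says a mother's score is entered once per twin. The questionnaires go to all mothers, a maternal number exists, and the details are left to an analysis plan that is not shown. The unit of record and the variance method are ordinary content for that plan.

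Much of this stands. A reader might infer that the protocol prescribes double counting, or that the reported intervals will be wrong. The documents do not support that: the error arises only if the sentence is applied literally and dependence is ignored. Exact duplication is also certain only for the WCI. The twin share is assumed, and the share that matters counts only pairs in which both neonates contribute a day-28 record. Deaths and losses can bring that below the enrolled share. Double weighting by itself is partly a choice of target, a neonate-weighted or a mother-weighted mean.

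What does not stand is that the protocol is merely silent. Sections 10.2.2 and 10.2.4 both name neonates for the secondary outcomes without exception, and the stated models deal with distribution and stratification factors, not dependence. An analysis plan with one record per mother would depart from that wording; one that follows it without a correction would have the problem shown above.

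**Conclusion.** The point holds conditionally and is of modest weight. Section 10.2.2, read as written and combined with the same-arm rule in section 5.6, gives a wrong standard error for the WCI unless dependence is handled. On an assumed 10% to 30% of analysed neonates in co-enrolled pairs, the naive standard error is about 5% to 12% too small and the real two-sided error is about 6% to 9%. A MIRI scored once per mother would be affected as the WCI is. A MIRI scored per infant would be affected less: 5.6% to 6.8% if the within-pair correlation were 0.5. The protocol does not allow the size to be fixed more closely.

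The point covers two secondary outcomes. It should not be read as a finding on mortality or on the sample size. There the outcome belongs to each infant, so nothing is duplicated, and correlation between twins was not assessed here.

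**What to change.** Add to section 10.2.2 that the WCI, and the MIRI if scored once per mother, is analysed with one record per mother, identified by the maternal enrolment number from section 5.4.3. If the MIRI is scored per infant, say so and use variance clustered by mother. Because the adjusted analyses include the birthweight stratum (section 3.2.1) and twins can fall in different bands, also state which band a mother of twins takes.

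No new data are needed. Before deaths and losses, 2188 neonates would give 2188(1 − t/2) maternal records: 2079, 1969 and 1860 at t = 10%, 20% and 30%. Relative to the naive analysis the interval widens by the factor 1/√(1 − t/2), that is by 2.6%, 5.4% and 8.5%. This is less than the 4.9%, 9.5% and 14.0% needed to correct the duplicated-record analysis. The wording should be settled before unblinding.
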